2 ETHICAL CONSIDERATIONS

2.1 Good Clinical Practice

This study will be conducted in accordance with Good Clinical Practice (GCP), as defined by the International Conference on Harmonisation (ICH) and in accordance with the ethical principles underlying European Union Directive 2001/20/EC and the United States Code of Federal Regulations, Title 21, Part 50 (21CFR50).

The study will be conducted in compliance with the protocol. The protocol and any amendments and the subject informed consent will receive Institutional Review Board/Independent Ethics Committee (IRB/IEC) approval/favorable opinion prior to initiation of the study.

All potential serious breaches must be reported to BMS immediately. A serious breach is a breach of the conditions and principles of GCP in connection with the study or the protocol, which is likely to affect, to a significant degree, the safety or physical or mental integrity of the subjects of the study or the scientific value of the study.

Study personnel involved in conducting this study will be qualified by education, training, and experience to perform their respective task(s).

This study will not use the services of study personnel where sanctions have been invoked or where there has been scientific misconduct or fraud (eg, loss of medical licensure, debarment).

2.2 Institutional Review Board/Independent Ethics Committee

Before study initiation, the investigator must have written and dated approval/favorable opinion from the IRB/IEC for the protocol, consent form, subject recruitment

materials/process (eg, advertisements), and any other written information to be provided to subjects. The investigator or sponsor should also provide the IRB/IEC with a copy of the Investigator Brochure or product labeling, information to be provided to subjects and any updates.

The investigator or sponsor should provide the IRB/IEC with reports, updates and other information (eg, expedited safety reports, amendments and administrative letters) according to regulatory requirements or institution procedures.

2.3 Informed Consent

Investigators must ensure that subjects, or, in those situations where consent cannot be given by subjects, their legally acceptable representatives, are clearly and fully informed about the purpose, potential risks, and other critical issues regarding clinical studies in which they volunteer to participate.

BMS will provide the investigator with an appropriate (ie, Global or Local) sample informed consent form which will include all elements required by ICH, GCP and applicable regulatory requirements. The sample informed consent form will adhere to the ethical principles that have their origin in the Declaration of Helsinki.

Investigators must:

- 1) Provide a copy of the consent form and written information about the study in the language in which the subject is most proficient prior to clinical study participation. The language must be non-technical and easily understood.
- 2) Allow time necessary for subject or subject's legally acceptable representative to inquire about the details of the study
- 3) Obtain an informed consent signed and personally dated by the subject or the subject's legally acceptable representative and by the person who conducted the informed consent discussion.
- 4) Obtain the IRB/IEC's written approval/favorable opinion of the written informed consent form and any other information to be provided to the subjects, prior to the beginning of the study, and after any revisions are completed for new information.
- 5) If informed consent is initially given by a subject's legally acceptable representative or legal guardian, and the subject subsequently becomes capable of making and communicating their informed consent during the study, then consent must additionally be obtained from the subject.
- 6) Revise the informed consent whenever important new information becomes available that is relevant to the subject's consent. The investigator, or a person designated by

the investigator, should fully inform the subject or the subject's legally acceptable representative or legal guardian, of all pertinent aspects of the study and of any new information relevant to the subject's willingness to continue participation in the study. This communication should be documented.

The consent form must also include a statement that BMS and regulatory authorities have direct access to subject records.

The rights, safety, and well-being of the study subjects are the most important considerations and should prevail over interests of science and society.

[figure not shown]
3 INVESTIGATIONAL PLAN

3.1 Study Design and Duration

Figure 3.1: Study Design

Stable dose of metformin (≥ 1500 mg) for ≥ 8 weeks Screening A1_c $\geq 8\% \leq 12\%$

Metformin IR and XR will be switched to the **nearest multiple of Metformin XR 500 mg tablets at week** -4

Randomization

3.2 Post Study Access to Therapy

At the end of the study, the sponsor will not continue to supply study drug to subjects/investigators unless the sponsor chooses to extend the study. The investigator should ensure that the subject receives appropriate standard of care to treat the condition under study.

3.3 Study Population

For entry into the study, the following criteria MUST be met prior to the visit at week -4.

3.3.1 Inclusion Criteria

1) Signed Written Informed Consent

a) Subjects must be willing and able to give signed and dated written informed consent.

2) Target Population

a) Subjects with T2DM with inadequate glycemic control, defined as a central laboratory HbA1c \ge 8.0 and \le 12.0 % obtained at the screening visit.

Note: At Week -4 a qualification check will be performed and subjects will be excluded, if their FPG is > 270 mg/dl. A re-test will be permitted within 7 days if the initial result was > 270mg/dl but < 300mg/dl. Subjects will be excluded if the mean value of the Week -4 result and the re-test result is > 270mg/dl.

- b) Stable metformin therapy for at least 8 weeks prior to screening at a dose ≥ 1500 mg per day.
- c) C-peptide $\geq 1.0 \text{ ng/mL} (0.34 \text{ nmol/L})$ at screening visit
- d) BMI $\leq 45.0 \text{ kg/m}^2$ at the screening visit

3) Age and Reproductive Status

- a) Men and women, aged ≥ 18 years old at time of screening visit.
- b) Women of childbearing potential (WOCBP) must be using an acceptable method of contraception to avoid pregnancy throughout the study in such a manner that

the risk of pregnancy is minimized. See Section 3.3.3 for the definition of WOCBP.

- c) WOCBP must have a negative serum or urine pregnancy test (minimum sensitivity 25 IU/L or equivalent units of HCG) within 24 hours prior to the start of investigational product.
- d) Women must not be breastfeeding.
- e) Sexually active fertile men must use effective birth control if their partners are WOCBP.

3.3.2 Exclusion Criteria

1) Target Disease Exceptions

- a) History of diabetes insipidus.
- b) Symptoms of poorly controlled diabetes that would preclude participation in this trial including but not limited to marked polyuria and polydipsia with greater than 10% weight loss during the 3 months prior to screening, or other signs and symptoms.
- c) History of diabetic ketoacidosis or hyperosmolar nonketotic coma.

2) Medical History and Concurrent Diseases

- a) History of bariatric surgery or lap-band procedure within 12 months prior to screening.
- b) Any unstable endocrine, psychiatric or rheumatic disorders as judged by the Investigator.
- c) Subject who, in the judgment of the Investigator, may be a risk for dehydration or volume depletion that may affect the interpretation of efficacy or safety data
- d) Subject is currently abusing alcohol or other drugs or has done so within the last 6 months.

Acute vascular event:

e) Uncontrolled hypertension defined as systolic blood pressure (SBP) \ge 160 mmHg and diastolic blood pressure (DBP) \ge 100 mmHg.

Note: Subjects with SBP \geq 160mmHg and < 180mmHg or a DBP \geq 100 mmHg and < 110mmHg will be able to enter the lead-in period, provided their hypertension treatment is adjusted as deemed appropriate by the investigator. These subjects can not be randomized if they meet the blood pressure exclusion criterion of SBP \geq 160 mmHg or DBP \geq 100 mmHg measured at Day 1.

- f) Cardiovascular Disease within 3 months of the screening visit [ie myocardial infarction, cardiac surgery or revascularization (CABG/PTCA), unstable angina, stroke or transient ischemic attack (TIA).
- g) Congestive heart failure as New York Association (NYHA) class IV (see Appendix 1), unstable or acute congestive heart failure. Note: eligible patients with congestive heart failure, especially those who are on diuretic therapy, should have careful monitoring of their volumes status throughout the study.

Renal Diseases:

- h) Moderate or severe impairment of renal function [defined as eGFR $< 60 \text{mL/min}/1.73 \text{ m}^2$ (estimated by MDRD) or serum creatinine (Scr) $\ge 1.5 \text{ mg/dL}$ in males or $\ge 1.4 \text{ mg/dL}$ in females]
- i) Conditions of congenital renal glucosuria.

Hepatic Diseases:

j) Significant hepatic disease, including, but not limited to, chronic active hepatitis and/or severe hepatic insufficiency, including subjects with ALT and/or AST > 3x ULN and or Total Bilirubin 2.5x ULN.

Hematological/Oncological Disease/Conditions:

- k) History of hemoglobinopathy, with the exception of sickle cell trait (SA) or thalassemia; or chronic or recurrent hemolysis.
- 1) Malignancy within 5 years of the screening visit (with the exception of treated basal cell or treated squamous cell carcinoma).
- m) Known immunocompromised status, including but not limited to, individuals who have undergone organ transplantation or who are positive for the human immnodeficiency virus.
- n) Donation of blood or blood products to a blood bank, blood transfusion, or participation in a clinical study requiring withdrawal of > 400 mL of blood during the 6 months prior to the screening visit.

Prohibited Treatment and Therapies:

- Administration of any antihyperglycemic therapy, other than metformin, for more than 14 days (consecutive or not) during the 12 weeks prior to screening, as well as previous participation in any DDP-4 or SGLT2 inhibitor trial is an exclusion criterion.
- p) Current treatment with potent cytochrome P450 3A4/5 inhibitors (in countries where dose adjustment would be required by the saxagliptin label).
- q) Administration of any other investigational drug or participation in any interventional clinical studies within 30 days of planned screening to this study.

3) Physical and Laboratory Test Findings

- a) Hemoglobin ≤ 11.0 g/dL (110 g/L) for men; hemoglobin ≤ 10.0 g/dL (100 g/L) for women
- b) Male subjects with microscopic hematuria present at week -6 or -4 AND no common cause that can be confirmed. Male subjects with a confirmed common cause can be randomized with a documented negative microscopic urinalysis. NOTE: Female subjects with hematuria can be randomized, but should be investigated according to local standards and best clinical practices. (See Appendix 3)

- c) Other central laboratory test findings:
 - Abnormal free T4 vales. Abnormal thyroid stimulating hormone (TSH) value at screening will be further evaluated by free T4. Subjects with abnormal free T4 values will be excluded.
 - Positive for hepatitis B surface antigen
 - Positive for anti-hepatitis C virus antibody

4) Allergies and Adverse Drug Reaction

a) Subjects who have contraindications to therapy as outlined in the saxagliptin and dapagliflozin Investigator Brochure, the local saxagliptin or dapagliflozin package insert or the local metformin package insert, including current treatment with potent cytochrome P450 3A4/5 inhibitors (in countries where dose adjustment would be required by the local saxagliptin label).

5) Sex and Reproductive Status

a) Women who are pregnant.

6) Other Exclusion Criteria

- a) Prisoners or subjects who are involuntarily incarcerated.
- b) Subjects who are compulsorily detained for treatment of either a psychiatric or physical (eg, infectious disease) illness.
- c) Subjects on a commercial weight loss program with ongoing weight loss, or on an intensive exercise program.
- d) Employees of BMS, AstraZeneca (AZ), or their relatives.
- e) Subject with any condition which, in the judgment of the Investigator, may render the subject unable to complete the study or which may pose a significant risk to the subject.
- f) Subject is a participating investigator, study coordinator, employee of an investigator or immediate family member of any of the aforementioned.

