- To compare the mean change from baseline in AUC of glucose, AUC insulin, AUC C-peptide and AUC glucagon obtained during a MTT with concurrent addition of saxagliptin and dapagliflozin to metformin vs. the addition of placebo and saxagliptin to metformin and vs. the addition of placebo plus dapagliflozin to metformin after 24 weeks of double-blind treatment.
- To compare the mean percent change from baseline in fasting serum lipids (Total-C, LDL-C, HDL-C, TG) with concurrent addition of saxagliptin and dapagliflozin to metformin vs. the addition of placebo and saxagliptin to metformin and vs. the addition of placebo plus dapagliflozin to metformin during the double-blind treatment period.

Study Design:

Figure 1: Study Design

Stable dose of metformin ($\geq 1500 \text{ mg}$) for ≥ 8 weeks Screening A1_c $\geq 8\% \leq 12\%$

Metformin IR or XR will be switched to the nearest multiple of Metformin XR 500 mg tablets at week -4

Day 1 Randomization

Study Population:

Inclusion:

- Men and women, aged ≥ 18 years old at time of screening visit
- Subjects with T2DM with inadequate glycemic control defined as central laboratory HbA1c \ge 8.0 and \le 12.0 % at the screening visit.
- Stable metformin therapy for at least 8 weeks prior to screening at a dose \geq 1500 mg per day
- C-peptide \geq 1.0 ng/mL (0.34 nmol/L) at screening visit
- BMI $\leq 45.0 \text{ kg/m}^2$ at the screening visit

Exclusion:

- Moderate or severe impairment of renal function [defined as eGFR <60mL/min/1.73 m² (estimated by MDRD) or serum creatinine (Scr) ≥ 1.5 mg/dL in males or ≥ 1.4 mg/dL in females]
- Uncontrolled hypertension defined as systolic blood pressure (SBP) ≥ 160 mmHg and/or diastolic blood pressure (DBP) ≥ 100 mmHg

Note: Subjects with SBP \geq 160mmHg and < 180mmHg or a DBP \geq 100 mmHg and < 110 mmHg will be able to enter the lead-in period, provided their hypertension treatment is adjusted as deemed appropriate by the investigator. These subjects can not be randomized if they meet the blood pressure exclusion criterion of SBP \geq 160 mmHg or DBP \geq 100 mmHg measured at Day 1.

- Cardiovascular diseases within 3 months of the screening visit
- Significant hepatic disease, including, but not limited to, chronic active hepatitis and/or severe hepatic insufficiency, including subjects with ALT and/or AST > 3x ULN and or Total Bilirubin > 2.5xULN.

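### Exclusion criterion 2e requires both blood pressure limits to be exceeded, contradicting the synopsis and its own Note, so isolated SBP ≥ 180 or isolated DBP ≥ 110 mmHg is handled inconsistently

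*Protocol*

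**What the plan says.** The blood pressure exclusion is stated three times, always with limits of 160 mmHg systolic and 100 mmHg diastolic, but with different connectives.

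- **Section 3.3.2, criterion 2e:** "160 mmHg and diastolic blood pressure (DBP" ≥ 100 mmHg. Both limits must be met.
- **Synopsis, Exclusion:** "160 mmHg and/or diastolic blood pressure (DBP" ≥ 100 mmHg. Either limit is enough.
- **Note under 2e, repeated in the synopsis:** "These subjects can not be randomized if they meet the blood pressure exclusion criterion of SBP" ≥ 160 or DBP ≥ 100 at Day 1. Either limit is enough, and the Note presents this as the exclusion criterion itself.

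The Note also makes an allowance. Subjects with SBP 160 to < 180 or DBP 100 to < 110 mmHg "will be able to enter the lead-in period, provided their hypertension treatment is adjusted as deemed appropriate by the investigator".

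Section 3.3 fixes when entry criteria apply: "the following criteria MUST be met prior to the visit at week -4". Section 3.3.2.1 (Randomization Criteria) lists only an FPG limit. Table 5.1 schedules seated blood pressure at Week -6 and Day 1, but not at Week -4, and schedules the review of eligibility criteria at Week -6.

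**The concern.** An eligibility rule that serves subject safety should give one answer for one patient. Here a site reading 2e and a site reading the synopsis can reach opposite answers at screening, and each can point to the protocol. The protocol does not say which text takes precedence.

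The connective in 2e also conflicts with the Note directly beneath it. If both limits had to be exceeded, a subject at 170/90 would not meet the criterion and would need no permission to enter lead-in. The Note nevertheless grants that permission, on condition that treatment is adjusted.

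At stake is whether subjects with a marked elevation of one limb enter lead-in, whether any treatment-adjustment condition applies to them, and whether anything expressly stops them at Day 1. Under Table 5.1, a subject passed at Week -6 has no further scheduled blood pressure measurement until Day 1.

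**Working it through.** The point concerns wording and involves no sample-size or power figure. The check applies each version of the criterion, together with the Note, to the same readings.

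**Rules (mmHg)**

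- 2e as written: excluded if SBP ≥ 160 **and** DBP ≥ 100.
- Synopsis: excluded if SBP ≥ 160 **or** DBP ≥ 100, or both.
- Note (same in both places): may enter lead-in, with treatment adjusted, if 160 ≤ SBP < 180 **or** 100 ≤ DBP < 110.

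**Grid** of SBP 150, 170, 190 by DBP 90, 105, 115:

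| Reading | Meets 2e | Meets synopsis | In a Note band | Outcome under 2e + Note | Outcome under synopsis + Note |
|---|---|---|---|---|---|
| 150/90 | no | no | no | enters | enters |
| 150/105 | no | yes | yes | enters, treatment adjusted | enters, treatment adjusted |
| **150/115** | no | yes | no | **enters, no condition** | **excluded** |
| 170/90 | no | yes | yes | enters, treatment adjusted | enters, treatment adjusted |
| 170/105 | yes | yes | yes | enters, treatment adjusted | enters, treatment adjusted |
| 170/115 | yes | yes | yes (SBP) | enters, treatment adjusted | enters, treatment adjusted |
| **190/90** | no | yes | no | **enters, no condition** | **excluded** |
| 190/105 | yes | yes | yes (DBP) | enters, treatment adjusted | enters, treatment adjusted |
| 190/115 | yes | yes | no | excluded | excluded |

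The bare definitions differ in 4 of 9 cells: 150/105, 150/115, 170/90 and 190/90. With the Note applied, 150/105 and 170/90 come out the same and 2 of 9 cells still differ. Those two represent:

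- SBP ≥ 180 with DBP < 100 (for example 185/95);
- DBP ≥ 110 with SBP < 160 (for example 150/115).

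The grid shows where the rules diverge. It is not an estimate of how many subjects are affected. The rows 170/115 and 190/105 follow the literal *or* of the Note's bands; because the Note is the same in both places, they do not separate the two versions.

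**Does Day 1 close the gap?** The Note's bar begins with a reference to these subjects, meaning those it has just admitted through the bands. A subject who entered at 185/95 or 150/115 under 2e is not one of them. Section 3.3.2.1 adds no blood pressure criterion. If sites applied the Day 1 *or* rule to everyone, it would stop any such subject whose pressure was still elevated, but the text does not say that it applies to everyone.

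**The case against.** The strongest reply is that the intended meaning can be recovered. The synopsis and the Note both use the either-limb form, and anyone reading 2e meets the Note in the same item. Exposure is also limited. Only metformin XR is dispensed at Week -4, no blinded drug is given before Day 1, and blood pressure is measured again on Day 1. An investigator may also exclude a subject with any condition "which may pose a significant risk to the subject" (section 3.3.2, item 6e).

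Much of this stands, and it keeps the point narrow. It does not settle it. Item 6e is discretionary and is not a blood pressure rule, and the Day 1 bar does not expressly reach the subjects concerned.

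A reader might infer more than the document supports:

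- **That every subject with one limb elevated is classified differently.** This overlooks the Note, which appears in both places. At 150/105 or 170/90 the subject may enter lead-in with treatment adjusted and faces the Day 1 bar under either text.
- **That the error causes subjects to be lost at Day 1 after weeks of lead-in.** That is how the Note's allowance operates. It happens to subjects in the bands under both versions, and changing the connective would not prevent it.
- **That sites will in fact recruit different populations.** All sites hold the same document, and nothing in it shows how they would resolve the conflict.

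**Conclusion.** The contradiction is real and lies in current text: the document history lists only the original protocol. Criterion 2e disagrees with the synopsis and with its own Note.

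Its practical reach is limited to isolated SBP ≥ 180 mmHg (DBP < 100) and isolated DBP ≥ 110 mmHg (SBP < 160). The synopsis excludes these subjects at screening. Criterion 2e as written admits them without the treatment-adjustment condition attached to milder elevations, and no text expressly stops them at Day 1. The protocol gives no figure from which to estimate how many such subjects would be screened.

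This rests on reading 2e literally and on reading the Day 1 sentence as covering only subjects admitted through the Note's bands. If the Day 1 rule were meant for all subjects, the gap would be confined to screening and lead-in for anyone still elevated at Day 1.

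The consequence is for eligibility and subject safety. Sample size, power, type I error and the primary HbA1c analysis are unaffected.

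**What to change.** Reconcile criterion 2e, its Note and the synopsis so that one definition of uncontrolled hypertension appears throughout. The synopsis and the Note already share the either-limb form and 2e is the exception, but the sponsor must decide which definition is meant.

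In the same correction:

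- keep the Note's lead-in allowance explicit as a separate provision, so that a single definition is not read as overriding it;
- state whether the Day 1 blood pressure bar applies to all subjects or only to those admitted through the allowance, and put that statement in section 3.3.2.1 as well.

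The cost is a short text correction in 2e, the Note, section 3.3.2.1 and, where needed, the synopsis. No change to the design, sample size or analysis follows.

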3.3.2.1 Randomization Criteria

Exclusion:

• FPG >270mg/dl as measured at Week -4

Note: At Week -4 a qualification check will be performed and subjects will be excluded, if their FPG is > 270 mg/dl. A re-test will be permitted within 7 days if the initial result was > 270 mg/dl but < 300mg/dl. Subjects will be excluded if the mean value of the Week -4 result and the re-test result is > 270 mg/dl.

Eligibility criteria for this study have been carefully considered to ensure the safety of the study subjects and to ensure that the results of the study can be used. It is imperative that subjects fully meet all eligibility criteria.

3.3.3 Women of Childbearing Potential

Women of childbearing potential include any female who has experienced menarche and who has not undergone successful surgical sterilization (hysterectomy, bilateral tubal ligation, or bilateral oophorectomy) or is not postmenopausal. Post menopause is defined as:

- Amenorrhea \geq 12 consecutive months without another cause and a documented serum follicle stimulating hormone (FSH) level > 35 mIU/mL or
- Women with irregular menstrual periods and a documented serum follicle stimulating hormone (FSH) level > 35 mIU/mL or (NOTE: FSH level testing is not required for women \ge 62 years old with amenorrhea of \ge 1 year)
- Women on hormone replacement therapy (HRT) who have prior clinical evidence of menopause based on any of the criteria above.

Women who are using oral contraceptives, other hormonal contraceptives (vaginal products, skin patches, or implanted or injectable products), or mechanical products such as an intrauterine device or barrier methods (diaphragm, condoms, spermicides) to prevent pregnancy, or are practicing abstinence or where their partner is sterile (eg, vasectomy) should be considered to be of childbearing potential.

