5 STUDY ASSESSMENTS AND PROCEDURES

5.1 Flow Chart/Time and Events Schedule

Table 5.1:Flow Chart for CV181169											
Procedure	Screening Period	Lead- In Period			Dou		nd Treatment Pe vindow ± 5days		Notes		
	WK (-6)WK (-4)Day 1WK 6WK 12WK 18WK S Term							Rescue / Early Treatment Discontinuation			
Eligibility Assessments											
Obtain Informed Consent	Х										
Review Medical History	Х										
Review Eligibility Criteria	Х										
Review Randomization Criteria			X								

Table 5.1:									
Procedure	Screening Period	Lead- In Period	Notes						
	WK (-6)	WK (-4)	Day 1	WK 6	WK 12	WK 18	WK 24/ Study Termination	Rescue / Early Treatment Discontinuation	
General Procedures									
Brief Physical Examination		X	Х	Х	Х	Х			
Complete Physical Examination	Х						Х	Х	
Body Weight	Х	X	Х	Х	Х	Х	Х	Х	
Seated Blood Pressure and Heart Rate	Х		X	X	Х	X	Х	Х	
Height	Х								
Body Mass Index (BMI)	Х								
Waist Circumference	Х		Х				Х		
12-Lead ECG			X				X*	X*	* Only 2 ECGs performed/subject. ECG is not required at Wk 24 if subject has been rescued or discontinued from treatment prior to Week 24

Saxagliptin and Dapagliflozin and

CV181169 Clinical Protocol

Saxagliptin	and	Dapagliflozin	

and

Table 5.1:	Flow Chart	for CV1	81169						
Procedure	Screening Period	Lead- In Period			Dou	ble-Blin Visit v	Notes		
		WK (-4)	Day 1	WK 6	WK 12	WK 18	WK 24/ Study Termination	Rescue / Early Treatment Discontinuation	
Review Concomitant Medications / Procedures	X	X	X	X	X	X	Х	Х	
Contact IVR system	X	X	X	X	X	X	X*	X**	* Call to register study termination only **Call at Rescue/ETD visit only if drug re-supply required.
Provide Diet and Exercise Counseling	Х	Х	Х	Х	X	X		Х	
Provide Glucose Meter and Supplies / Instructions		X	X	Х	Х	Х		X*	*Only if required
Provide logs / Instructions		Х	Х	Х	Х	Х			
Review study logs			Х	Х	Х	Х	Х	Х	

Table 5.1:									
Procedure	Screening Period	Lead- In Period			Dou	ble-Bli Visit v	Notes		
	WK (-6)	WK (-4)	Day 1	WK 6	WK 12	WK 18	WK 24/ Study Termination	Rescue / Early Treatment Discontinuation	
Safety Assessment									
Assess Adverse Events, Hypoglycemia Episodes		X	X	X	X	X	Х	X	
Central Laboratory			•		•				
Pregnancy Test (urine) WOCBP only	Х	X	X	X	X	X	X	X	Home pregnancy test kits sent home with WOCBP to perform pregnancy tests between visits and record resul in log book
Blood & Urine Standard Safety Laboratory Panels	Х	X	X	Х	Х	Х	Х	Х	

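### Section 3.3.3 lets a woman who still has irregular periods count as postmenopausal on one FSH result, which removes every contraception and pregnancy-testing duty for a sexually active woman using no protection.

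*Protocol*

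**What the plan says.** Section 3.3.3 excludes postmenopausal women from the class of women of childbearing potential (WOCBP) and defines post menopause by three bullets.

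- **Amenorrhea route.** Menses must have been absent for at least "12 consecutive months without another cause and a documented serum follicle stimulating hormone (FSH) level > 35 mIU/mL or" one of the other bullets must apply.
- **Irregular-periods route.** "Women with irregular menstrual periods and a documented serum follicle stimulating hormone (FSH) level > 35 mIU/mL or" the next bullet. A note inside this bullet waives FSH testing from age 62, but only with at least one year of amenorrhea.
- **Hormone replacement route.** "Women on hormone replacement therapy (HRT) who have prior clinical evidence of menopause based on any of the criteria above".

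A closing paragraph returns some women to WOCBP status: users of hormonal or mechanical contraception, and women who "or are practicing abstinence or where their partner is sterile (eg, vasectomy) should be considered to be of childbearing potential".

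The duties that depend on this status are stated elsewhere:

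- Section 3.3.1, criterion 3b: "Women of childbearing potential (WOCBP) must be using an acceptable method of contraception to avoid pregnancy throughout the study".
- Section 3.3.1, criterion 3c: "WOCBP must have a negative serum or urine pregnancy test", in the 24 hours before investigational product is started.
- Table 5.1 (Section 5.1): the row is headed "Pregnancy Test (urine) WOCBP only", and its note adds "Home pregnancy test kits sent home with WOCBP to perform pregnancy tests between visits".
- Section 3.4.2: the duty to contact the investigator at once if pregnancy is suspected is also placed on WOCBP only.

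**The concern.** The first two routes use the same FSH cut-off, but only the first also asks for a year without menses. The second asks for irregular bleeding instead, which means that the woman is still menstruating. The hormone replacement route refers back to any of the earlier criteria, so it inherits the looser one.

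The closing paragraph makes the result odd. Women who already have some protection against pregnancy, or who are abstinent, keep all the safeguards. A woman with irregular periods who is sexually active, uses nothing and has a fertile partner keeps none.

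What is at stake is undetected exposure of a pregnancy to study drug. Section 4.3 describes dapagliflozin 10 mg as investigational, and Section 6.1 requires pregnancies to be handled as serious adverse events. The same definition also governs criterion 3e, under which fertile male subjects need birth control only if their partner is a WOCBP.

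**Working it through.** There is no stated figure to reproduce. The check follows the definition through to each rule that depends on it.

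**Step 1: compare the routes at the same FSH value, above 35 mIU/mL.**

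| Woman | Route | Classed as postmenopausal? |
|---|---|---|
| 11 months of amenorrhea, periods previously regular | Amenorrhea (needs at least 12 months) | No |
| Bled last month, irregular cycles | Irregular periods | Yes |
| Aged 62 or over, amenorrhea of at least 1 year | Note (FSH waived) | Yes |

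The Protocol asks for a year without menses in the first and third cases, and for none in the second.

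**Step 2: see whether the closing paragraph brings her back.** It applies if she uses hormonal or mechanical contraception, is abstinent, or has a sterile partner. A sexually active non-user with a non-sterile partner meets none of these conditions and stays outside WOCBP.

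**Step 3: list what she loses and what she keeps.**

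| Rule | Applies to | Reaches her? |
|---|---|---|
| Contraception (3.3.1, 3b) | WOCBP | No |
| Test before first dose (3.3.1, 3c) | WOCBP | No |
| Clinic and home urine tests (Table 5.1) | WOCBP | No |
| Prompt contact if pregnancy is suspected (3.4.2) | WOCBP | No |
| Pregnancy exclusion (3.3.2, 5a) | All women | Yes, if the pregnancy is known |
| Mandatory discontinuation (3.5) | All subjects | Yes, once the pregnancy is known |
| Reporting and follow-up (6.4) | All subjects | Yes, once the pregnancy is known |

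The last three rules act on a known pregnancy, and no test is scheduled that would reveal one in her.

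**Step 4: size the difference in testing.** The pregnancy-test row of Table 5.1 has eight marks: Week -6, Week -4, Day 1, and Weeks 6, 12, 18 and 24 (seven scheduled visits), plus Rescue/Early Treatment Discontinuation (conditional).

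- WOCBP: 7 scheduled clinic tests, 1 conditional test, and home tests. From Day 1 the clinic interval is 6 weeks × 7 = 42 days.
- Woman in the gap: 0 tests. The untested double-blind period is 24 weeks × 7 = 168 days.

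**The case against.** The strongest reply is that this is a deliberate choice among alternatives. Criteria joined by "or" need not be equally strict, and the Protocol gives no conception rate for women with irregular periods and a raised FSH, and no reproductive risk for either drug. That is true, and it is why no estimate of harm can be given. It does not explain why the Protocol requires a year of amenorrhea at the same FSH level in one bullet, and even at age 62, but drops it for a woman who is still bleeding.

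The route is also narrow. FSH appears neither in Table 5.1 nor among the tests in Appendix 2, so a woman without a documented result cannot use the route and remains a WOCBP. This limits the numbers. However, the bullet sets no date or source for the result, so an old outside value would qualify.

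Discretionary safeguards remain. The investigator may exclude a subject at significant risk (3.3.2, 6e) or arrange unscheduled assessments (5.3.8.2). Contraindications in the Investigator Brochure or package inserts also exclude (4a). These reduce the concern, but a site that applies Section 3.3.3 correctly has no prompt to use its discretion.

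Finally, the definition of WOCBP is loosely built. Read literally, its "or" could keep every unsterilized woman in the class. That reading would leave the postmenopausal definition with no purpose, so sites are unlikely to adopt it.

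**Conclusion.** The concern holds. Followed as written, Section 3.3.3 leaves a real but narrow safety gap for women who have irregular periods and one FSH above 35 mIU/mL, are sexually active, use no contraception and have a non-sterile partner. For each such woman the schedule gives no pregnancy test in place of seven, and no required contraception over 168 days of dosing.

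Two assumptions support this. The first is that the postmenopausal bullets are meant to remove women from the WOCBP class. The second is that a woman who still menstruates irregularly has some chance of conceiving; the Protocol gives no figure, but its own amenorrhea requirement in the first bullet points the same way. The number affected is not stated. It could be very few of the 516 to be randomized, or none. This is a matter of subject safety that should be corrected. It changes no efficacy result, power or type I error.

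**What to change.** Amend Section 3.3.3 as follows:

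1. Delete the irregular-periods bullet, so that such women are WOCBP. Adding 12 months of amenorrhea to it would also close the gap, but would only repeat the first bullet and clash with its own reference to irregular periods.
2. Move the note that waives FSH testing from age 62 to the amenorrhea bullet, where it belongs.
3. Limit the hormone replacement bullet to women who met the amenorrhea criterion before starting that therapy.

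The cost is one amended definition. A few more women will need contraception, the urine tests already in Table 5.1 and the home kits already supplied under Section 5.2. No change to the sample size or analysis is needed.
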